#### 3. STUDY ENDPOINTS

The primary effectiveness endpoint is the absolute time to hemostasis (elapsed from randomization), defined as the absolute time when there is no detectable bleeding at the Target Bleeding Site (TBS).

In addition, the following secondary endpoints will be included in this study:

- Haemostasis at 4, 7 and 10 minutes following randomization;
- Incidence of treatment failures (defined as haemostasis not achieved within 10 minutes or bleeding at the TBS during the ten-minute observational period that requires further hemostatic measures, other than re-application of the assigned hemostatic adjunct);
- Incidence of adverse events (including thrombotic events and events associated with TBS rebleeding);
- Proportion of subjects with no re-bleeding;
- Haemoglobin, Haematocrit, Platelets, Volume of blood loss, Volume of blood and blood products transfusions

#### 4. CHANGES IN THE CONDUCT OF THE STUDY OR PLANNED ANALYSIS

Not applicable.

#### 5. ANALYSIS SETS

The following three analysis sets defined:

- The Full analysis Set (FAS) consists of all randomized subjects (equivalent to the Intent-to-Treat [ITT] set);
- The Per-Protocol (PP) analysis set (Evaluable set) consists of all FAS subjects who have no major protocol deviations;
- The Safety analysis set consists of all subjects who received treatment.

Major protocol deviations are deviations that have an impact on the primary endpoint, or that have an impact on the randomization assignment. These will be determined prior to database lock.

The primary effectiveness endpoint will be analyzed using the FAS and the PP set. However, the primary analysis will be based on the FAS. The PP analysis will be considered confirmatory.

All secondary effectiveness endpoints (listed in section 8.3) will be analyzed using the FAS set, while safety endpoints (listed in section 9) will be analyzed using the Safety set.

Page 4 of 18 Version: AMENDMENT 1 Date: July 1, 2019

If any patients are mis-randomized (randomized to one treatment, but received the other), then data for the FAS will be summarized 'as randomized', and data for the safety set will be summarized 'as treated'.

If more than 2 patients are mis-randomized, then additional analyses for the FAS will be performed, with patients allocated to treatment groups 'as treated'. Patients who are mis-randomized will be considered major protocol deviations.

## 6. DEMOGRAPHIC AND OTHER BASELINE CHARACTERISTICS

## 6.1 Demographic and other baseline characteristics

Demographic and other baseline data will be summarized descriptively for subjects in each treatment group in the FAS set. The categorical data will be summarized descriptively by frequencies along with the associated percentages. The continuous data will be presented using summary statistics such as number of subjects, mean, standard deviation, minimum, median and maximum.

The following demographic variables will be summarized:

- Age;
- Gender;
- Race/ethnicity;
- Height;
- Weight;
- Body mass index;
- Indication of subject being of child bearing age.

In addition, the following screening and baseline data will be collected:

- Physical examination, including documentation of relevant medical and surgical history;
- Full blood count (FBC) with white blood cell differential, and coagulation parameters;
- Documentation of medical history and all concomitant medications during 24 hours prior to surgery;
- Review of inclusion / exclusion criteria to confirm subject eligibility.

#### 7. PROCEDURE DATA

Procedure data will be summarized descriptively for subjects in each treatment group in the FAS set. The categorical data will be summarized descriptively by frequencies along with the associated percentages. The continuous data will be presented using summary statistics such as number of subjects, mean, standard deviation, minimum, median and maximum.

The following procedure variables will be analyzed:

- Primary operative procedure;
- Operating room (OR) time;
- Procedure duration (from first incision to closure completion);
- Procedure duration from first incision to initiation of final fascial closure (when applicable);
- Specification of treatment to which subject is randomized;
- TBS length, width, area, and location, type of bleeding, and TBS tissue or parenchymal organ type;

Page 5 of 18

Version: AMENDMENT 1 Date: July 1, 2019

- Estimated intraoperative blood loss, blood or blood product transfusions from surgery through hospital discharge, and cell saver usage data;
- Primary method used to obtain hemostasis at the TBS;
- Surgical approach;
- For patients treated with EVICEL, approximate amount of EVICEL used (up to 10 minutes following randomization), number of EVICEL kits used, quantity per kit; in addition, for all EVICEL kit used type of tip, method of application, and size of kit;
- For patients treated with SURGICEL, number of kits used, indication of SURGICEL use according to IFU, approximated SURGICEL length and width used at the TBS, and SURGICEL area applied;
- Hemostasis assessment data, such as time from randomization to initial application of randomized hemostatic product, TBS hemostasis presence at 4, 7, and 10 minutes from randomization, absolute time to hemostasis (from randomization), and presence of any bleeding at TBS between 4 and 10 minutes following randomization;
- Bleeding/durability data, such as indication of any additional treatment use at the TBS, indication of any rebleeding, and, for all rebleeds treatment used for rebleed;
- Length of subject hospital stay (from hospital admission to hospital discharge, as well as from procedure to hospital discharge);
- Time from screening visit to hospital admission, time from baseline visit to hospital admission, time from screening visit to surgery, and time from baseline visit to surgery.

## 8. EFFECTIVENESS

#### 8.1 General methods of analysis

The Clinical Data Management and Biostatistics groups within Clinical Development at ETHICON will be responsible for the overall analysis of data from this protocol. All analyses/summaries will be produced using SAS® (Version 9.1 (EG) or later).

Data will be summarized descriptively for subjects in each treatment group in the FAS set. The categorical data will be summarized descriptively by frequencies along with the associated percentages. The continuous data will be presented using summary statistics such as number of subjects, mean, standard deviation, minimum, median and maximum.

#### 8.2 Primary effectiveness analysis

The primary effectiveness endpoint is the absolute time to hemostasis (elapsed from randomization), defined as the absolute time when there is no detectable bleeding at the Target Bleeding Site (TBS).

The primary effectiveness endpoint will be summarized descriptively by treatment group. The primary endpoint will also be summarized descriptively by treatment group and age group [Neonates (birth to 30 days), Infants and toddlers (31 days to <24 months), Children (2 to 11 years), and Adolescent (12 to <18 years)]. In addition, 95% distribution-free confidence intervals (CIs) for median absolute time to hemostasis will be reported separately for EVICEL and control groups.

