14.3 Record Retention	
15 CHANGES TO THE PROTOCOL	
15.1 Protocol Amendments	31
15.2 Clinical Trial Termination	31
15.3 Use of Information and Publication	32
16 ETHICON CONTACT DETAILS	33

Amendment 4: 08 January 2018

A Prospective, Randomized, Controlled Study Evaluating EVICEL® Fibrin Sealant as an Adjunct to Hemostasis During Abdominal, Retroperitoneal, Pelvic or Thoracic (Non-Cardiac) Surgery in Paediatric Patients

SYNOPSIS

OBJECTIVES:	To evaluate the safety and effectiveness of EVICEL® Fibrin Sealant (Human) as an adjunct to achieve haemostasis during surgery in paediatric patients.
STUDY DESIGN:	This is a prospective, randomized, controlled, clinical study comparing EVICEL® to SURGICEL®, as an adjunct to haemostasis when conventional methods of controlling bleeding are ineffective or impractical during surgery in paediatric patients.
	At least 40 qualified paediatric subjects with an appropriate mild or moderate Target Bleeding Site (TBS) will be randomized in a 1:1 allocation ratio to either EVICEL® or SURGICEL®. Haemostasis will be assessed at 4, 7 and 10 minutes from randomization.
	Subjects will be followed post-operatively through hospital discharge and at 30 days (±14 days) post-surgery.
TBS DEFINITION:	The TBS is the first actively bleeding site identified in the soft tissue or a parenchymal organ with mild or moderate bleeding, where conventional methods of control are ineffective or impractical, and an alternative method is required to achieve haemostasis.
	The TBS must be an area that can be visualised to assess haemostasis and where EVICEL® can be applied across the whole bleeding surface in a thin layer. (Refer to investigator's brochure.)
BLEEDING	Mild Bleeding: a TBS with a small area of capillary, arteriole or venule oozing.
SEVERITY:	Moderate Bleeding: a TBS with a larger area of capillary, arteriole, or venule oozing that presents a significant challenge because of the larger area involved, increasing the volume of blood loss, or a TBS with bleeding that is more pronounced than oozing, that could also come from a small artery or vein, but is not massive.

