2. STUDY OBJECTIVES

To evaluate the safety and haemostatic effectiveness of the EVICEL® versus SURGICEL® in controlling mild or moderate soft tissue or parenchymal organ bleeding during abdominal, pelvic, retroperitoneal or thoracic (non-cardiac) surgery.

The primary endpoint will be the absolute time to haemostasis, defined as the absolute time when there is no detectable bleeding at the Target Bleeding Site (TBS).

The secondary endpoints of this study include:

- Haemostasis at 4, 7 and 10 minutes following randomization;
- Incidence of treatment failure (defined as haemostasis not achieved within 10 minutes);
- Incidence of adverse events (including thrombotic events and events associated with TBS rebleeding);
- Proportion of subjects with no- rebleeding; and
- Haemoglobin, Haematocrit, Platelets, Volume of blood loss, Volume of blood and blood products transfusions.

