5 RANDOMIZATION

Randomization will be used to avoid bias in the assignment of treatment to each subject, to increase the likelihood that attributes of the subject are evenly balanced across treatment groups, and to enhance the validity of statistical comparisons across treatment groups.

ETHICON will provide each site with computer-generated randomization envelopes, each bearing the subject randomization number, and containing the treatment allocation.

Treatment will be assigned randomly to each subject on a 1:1 basis to either EVICEL® or SURGICEL® treatment.

In the event that a potential subject fails intra-operative criteria (i.e. no TBS identified, or an intra-operative exclusion), and is not randomized to the study, the unused randomization envelope should be returned to the series, and used for the next subject.

Given the difference between the EVICEL® and SURGICEL® treatment groups, it will not be possible for the surgeon to be blinded to the treatment. However, to avoid any bias in the conduct of the surgical procedure, randomization should only take place after completion of the following steps:

- 1. EVICEL® and SURGICEL® will be prepared and available in the sterile field in the operating room, ready for administration for each patient.
- 2. The investigator must perform the surgical procedure according to his/her standard of care.
- 3. Once the investigator encounters an appropriate soft tissue or parenchymal organ TBS related to the primary operative procedure, randomization should immediately take place.

-

⁵ See Appendix 1

Amendment 4: 08 January 2018

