## 2. STUDY DESIGN

This is a multi-centre, prospective, randomized, controlled, study in paediatric patients evaluating the safety and hemostatic effectiveness of EVICEL compared with SURGICEL® (SURGICEL) to control mild or moderate soft tissue bleeding or parenchymal organ bleeding during abdominal, pelvic, retroperitoneal or thoracic (non-cardiac) surgery for which standard methods of achieving haemostasis are ineffective or impractical.

At least 40 eligible pediatric subjects with an appropriate Target Bleeding Site (TBS), recruited from study centers within The European Union and Canada, will be randomized in a 1:1 allocation ratio to either EVICEL or SURGICEL treatment. Hemostasis will be assessed at 4, 7 and 10 minutes from randomization.

For this study, the TBS will be defined as the first actively bleeding site identified during the soft tissue or parenchymal organ dissection related to the primary operative procedure with challenging mild to moderate bleeding, where conventional methods of control (i.e. suture, ligature, cautery) have been deemed ineffective or impractical, and require an alternative method to achieve hemostasis. The randomly assigned treatment (EVICEL or SURGICEL) will be applied immediately at the actively bleeding TBS.

Randomization will be used to avoid bias in the assignment of treatment to each subject, to increase the likelihood that attributes of the subject are balanced across treatment groups, and to enhance the validity of statistical comparisons across treatment groups.

ETHICON will provide each site with computer-generated randomization envelopes, each bearing the subject randomization number, and containing the treatment allocation. Treatment, either EVICEL or SURGICEL, will be assigned randomly to each subject on a 1:1 basis. In the event that a potential subject fails intraoperative criteria (i.e. no TBS identified, or an intraoperative exclusion), and is not randomized to the study, the unused randomization envelope should be returned to the series, and used for the next subject. Given the difference between the two treatment groups, it will not be possible for the surgeon to be blinded to the treatment. However, to avoid any bias in the conduct of the surgical procedure, randomization should only take place after completion of the following steps:

- 1. EVICEL and SURGICEL will be prepared and available in the sterile field in the operating room, ready for administration for each patient.

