1.3.5	Operative data: EVICEL application summary – FAS	For all EVICEL kits used: type of tip, method of application, and size of kit used (all d)	G2

<sup>1 Shell: Example table from Appendix 1 (Shell tables). Letters refer to standard output, numbers to project specific output.  For Tables G1, G2, G3 notes will indicate if data is continuous or discrete.

No	Title of table/figure	Notes	Shell 
1.3.6	Operative data: Hemostasis assessments – FAS	Time from randomization to initial application of randomized hemostatic product (sec) (c), TBS hemostasis presence at 4, 7, and 10 minutes from randomization (d), absolute time to hemostasis (from randomization) (sec) (c), and presence of any bleeding at TBS between 4 and 10 minutes following randomization (d)	G2
1.3.7	Operative data: Bleeding/durability details - FAS	Indication of any additional treatment use at the TBS (d) and indication of any rebleeding (d)	G2
1.3.8	Operative data: Treatments for re-bleeding – FAS	For all rebleeds - treatment used for re-bleeding (d)	G2
1.3.9	Operative data timings and other durations – FAS	Time in operating room (min), length of procedure (from first incision to last suture/staple) (min), length of procedure measured as time from first incision to initiation of fascial closure (when applicable) (min), time from screening visit to hospital admission (days), time from baseline visit to hospital admission (days), time from screening visit to surgery (days), and time from baseline visit to surgery (days) (all c)	G2
2	Effectiveness data		
2.1	Primary endpoint: Absolute time to hemostasis, elapsed from randomization	Includes analysis by age group; Includes 95% CIs for median absolute time to hemostasis, reported separately for EVICEL and control groups	
2.1.1	Primary effectiveness analysis: Absolute time to hemostasis, elapsed from randomization – FAS	Continuous data	G2
2.1.2	Primary effectiveness analysis: Absolute time to hemostasis, elapsed from randomization – PP set (confirmatory analysis)	Continuous data	G2
2.2	Secondary effectiveness endpoints		
2.2.1	Haemostasis at 4 minutes following randomization – FAS	Discrete data Includes 95% CI for proportion of subjects with hemostasis at 4 minutes separately for each group, as well as 95% CI for the ratio of proportions	G2

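### The primary endpoint has no planned between-arm estimate, and the protocol's inference sentence for the secondary proportions has no reference value: both are cheap to put right

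*SAP*

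**What the plan says.** **Primary endpoint.** The protocol synopsis, Protocol 8.2 and 8.3.2 and SAP 8.2 all plan the same thing: descriptive summaries by arm and one 95% CI for the median in each arm. In SAP 8.2 the interval sentence reads "95% distribution-free confidence intervals (CIs) for median absolute time to hemostasis will be reported separately for EVICEL and control groups". SAP 10.2.2 repeats it for Table 14.2.1: "Includes 95% CIs for median absolute time to hemostasis, reported separately for EVICEL and control groups". Under SAP 8.1 the per-arm statistics are "number of subjects, mean, standard deviation, minimum, median and maximum". The visible text plans no difference, ratio, hazard ratio or test between arms for this endpoint.

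**Purpose.** Protocol 2 sets out to evaluate the "haemostatic effectiveness of the EVICEL® versus SURGICEL® in controlling mild or moderate soft tissue or parenchymal organ bleeding". The synopsis describes a "randomized, controlled, clinical study comparing EVICEL® to SURGICEL", and Protocol 5 gives as one reason for randomising "to enhance the validity of statistical comparisons across treatment groups". The objectives in the synopsis and in SAP 1 are not comparative; they speak of EVICEL as an adjunct to haemostasis.

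**Secondary proportions.** SAP 8.3 plans a Clopper-Pearson CI per arm and a score CI for the ratio P_E/P_C at 4, 7 and 10 minutes, and calls the summaries descriptive. Protocol 8.2 and 8.3.2 plan the same intervals but add that their lower limits will serve for inference. Neither section gives a null value or margin. Protocol 8.2 also sets a 5% level, should tests apply, and names none. SAP 8.5.3 lists multiplicity as not applicable, and SAP 4 records no change to the planned analysis.

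**The concern.** In a randomised trial, the contrast between arms is what randomisation protects. Here the primary endpoint gets less comparative information than the secondary ones. A reader of Tables 14.2.1.1 and 14.2.1.2 would see two medians with two separate intervals, and these do not combine into a 95% interval for the difference or ratio.

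A contrast could be worked out later from the per-arm n, mean and SD, or from the subject-level times in Listing 16.2.6.1. Its scale, method and handling of awkward times would then be chosen after the data are known, in a trial where the surgeon is not blinded.

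On the secondary proportions, the protocol announces inference without saying against what, while the SAP describes. A report could follow either.

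**Working it through.** **Inputs from the documents.** 1:1 allocation and at least 40 subjects, 20 per group (Protocol 8.1); two-sided 95% intervals (Protocol 8.2); distribution-free median CIs (SAP 8.2); times in seconds (SAP Table 14.1.3.6). The sample size comes without a calculation, so there is no planned figure to reproduce. The documents give no variance and no success rates.

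**Assumptions.** Lognormal times with the same log-SD in both arms (0.6, 0.8 or 1.0), no ties, and true time ratios EVICEL/SURGICEL of 1.0 and 0.50 (0.67 in step 4). Each setting in steps 2 and 3 was simulated 20,000 times.

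**1. What each planned median CI is.** With n = 20 and X ~ Binomial(20, ½), the interval from the 6th to the 15th ordered time has coverage 1 − 2·P(X ≤ 5) = 95.86%. The next narrower choice, 7th to 14th, covers only 88.47%.

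**2. What one between-arm estimate would give.** Form all 20 × 20 = 400 ratios of an EVICEL time to a SURGICEL time. The Hodges-Lehmann estimate is their median (on the log scale, the shift). The 95% limits are the 128th and 273rd ordered ratios. From the exact Mann-Whitney null distribution, coverage is 1 − 2·P(U ≤ 127) = 95.09% for untied times. Typical interval width:

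| Assumed log-SD | 95% CI: estimate ×/÷ |
|---|---|
| 0.6 | 1.48 |
| 0.8 | 1.69 |
| 1.0 | 1.92 |

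**3. Why two median CIs are a poor substitute (illustration only).**

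| True ratio | Log-SD | Median CIs do not overlap | Hodges-Lehmann CI excludes 1 |
|---|---|---|---|
| 1.0 | 0.6–1.0 | 0.3–0.4% | about 5% |
| 0.50 | 0.6 | about 48% | 93% |
| 0.50 | 0.8 | about 23% | 74% |
| 0.50 | 1.0 | about 12% | about 54% |

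Under these assumptions, a halving of time would leave the two intervals overlapping in roughly half to nearly nine-tenths of trials. The last column measures precision; it does not propose a test.

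**4. Times that need a stated rule.** Protocol 7.1.3.4 records absolute times after 10 minutes, and allows other haemostatic measures after 10 minutes or, if needed, sooner. SAP 8.5.1 does not impute missing primary times. Suppose the true ratio is 0.67 and the 4 slowest subjects of one arm have no time or needed other measures (a hypothetical case, 10,000 replicates, range over the three log-SDs):

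| Arm affected | Those subjects omitted | Those subjects ranked worst |
|---|---|---|
| SURGICEL | 0.80–0.91 | 0.61–0.64 |
| EVICEL | 0.50–0.56 | 0.71–0.73 |

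Omission favours the affected arm; worst-ranking counts against it. With one arm affected, each worst-ranked subject makes 20 of the 400 ratios extreme, and 127 ratios lie beyond each limit. Six such subjects (6 × 20 = 120) leave both limits finite; seven (140) make one limit unbounded.

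**5. The secondary lower limits.** Score limits for P_E/P_C are the values r at which (p_E − r·p_C)/SE_r = ±1.96, where SE_r is computed under r.

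- 18/20 versus 18/20: ratio 1.00 (0.76 to 1.31). The lower limit clears 0.7 but not 0.8.
- 18/20 versus 13/20: ratio 1.38 (0.99 to 2.11). It clears 0.9 but not 1.
- 18/20 in one arm alone: Clopper-Pearson lower limit 0.683, with no stated value to compare it to.

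The conclusion would therefore depend on a value that the protocol does not state. If all three ratio limits were read against 1 with no true difference, the chance that at least one exceeds 1 is 2.3% to 6.4%, for assumed 4/7/10-minute rates from 0.9/0.95/0.98 to 0.3/0.6/0.8.

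**The case against.** The strongest reply is that the trial is openly descriptive: no formal sample size, no interim analysis, multiplicity not applicable. Every place that specifies the primary analysis agrees, and two of the three statements of the objective are not comparative. A descriptive plan need not test anything. All of this stands. It does not rule out a contrast, however, because the same plan already gives the secondary proportions a between-arm ratio with a CI.

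Second, a reader might infer from step 3 that the plan judges the arms by overlap of the median CIs. No document says so. Those percentages describe what an informal comparison by eye would do under assumed variances.

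Third, the contrast is recoverable: roughly from the summary statistics, and fully from Listing 16.2.6.1 by anyone who has the report. That is correct. What would be missing is pre-specification.

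Fourth, the SAP leans clearly towards description for the secondary proportions. The synopsis carries no inference sentence, and the 5% level is conditional, so naming no test is consistent with it. This reduces the second part to a wording matter. It does not remove it: Protocol 8 has the SAP build on and add to the protocol's methods, and the SAP is silent on the inference sentence. SAP 9.4 does exclude inferential analysis, but it covers the Safety set and cannot be read as settling the effectiveness endpoints on the full analysis set.

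**Conclusion.** Both parts hold, as a cheap improvement and a minor reconciliation.

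1. The primary endpoint has no planned between-arm estimate. No stated figure is wrong, and the documents do not support reading this as an invalid design or as a demand for a hypothesis test. The textual gap rests on no assumption. The sizes do: 20 per arm, lognormal times, an assumed log-SD of 0.6 to 1.0 and no ties. The table shells are in an attachment that was not available; a contrast there is unlikely but cannot be excluded.

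2. The inference sentence in Protocol 8.2 and 8.3.2 lacks a reference value and does not fit the descriptive purpose. A reader might infer a serious false-positive risk. The figures do not bear that out: at most about 6.4% across three limits under the assumed rates, with no single limit above 2.7%.

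**What to change.** **(a) SAP 8.2 and Tables 14.2.1.1 and 14.2.1.2.** Add one Hodges-Lehmann ratio of times, EVICEL/SURGICEL (shift on the log scale, times in seconds), with a 95% CI, labelled as estimation and not a test. State that:

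- it uses all recorded times, including those after 10 minutes or after other haemostatic measures, and so describes time to haemostasis whatever further measures were used;
- if any subject has no recorded time or needed other measures, the same estimate is shown beside it with those subjects ranked worst, by giving them one common value longer than any recorded time;
- worst-ranking counts against the arm with more such subjects, and coverage is only nominal if times are tied.

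**(b) Protocol 8.2 and 8.3.2.** Replace the lower-limits sentence in both sections, and the 5% sentence in 8.2, with: *All confidence intervals are descriptive; no superiority or non-inferiority claim will be based on them.* If no further amendment is planned, put this sentence in SAP 8.3 and record it in SAP 4.

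**Cost.** A few SAP lines, one extra row in two existing tables, and a second row if worst-ranking is needed (in-text Table T3 already provides for a sensitivity summary). No new data are needed. Changing the protocol text means going through the amendment route in Protocol 15.1. The downside is a visibly wide interval.
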